7.3.2 Demographics and Other Characteristics

All baseline presentations will identify subjects with missing measurements. In tabulations of categorical variables, percentages are based on subjects with measurements.

7.3.2.1 Demographics and Other Baseline Characteristics

Demographic and other baseline characteristics (including disease characteristics) will be summarized by as-randomized treatment arm and overall for the treated subjects. Available demographic characteristics will also be summarized for subjects enrolled but not randomized.

Table 7.3.2.1-1: Demographic Characteristics

Characteristic	Summarized as	Categories
Gender	Categorical	Male, Female
Age	Continuous and Categorical	< 50 , ≥ 50 years
Race	Categorical	White, Black/African American, American Indian/Alaska Native, Asian, Native Hawaiian/Other Pacific Islander, Other
Ethnicity (US only)	Categorical	Hispanic/Latino Non Hispanic/Latino
Geographic Region	Categorical	Europe Asia Australia South America North America Africa

Table 7.3.2.1-2: Baseline Disease Characteristics

Characteristic	Summarized as	Categories
Plasma HIV-1 RNA	Continuous (log ₁₀ c/mL) and Categorical	<30,000c/mL 30,000 to < 100,000c/mL 100,000 to < 500,000c/ mL ≥ 500,000c/mL
CD4+ T-cell count	Continuous and Categorical	<50cells/mm ³ 50 to < 100cells/mm ³ 100 to < 200cells/mm ³ 200 to < 350cells/mm ³ 350 to < 500cells/mm ³ ≥ 500cells/mm ³
CD4+ T-cell percentage	Continuous	
CD8+ T-cell count	Continuous	
HIV-1 Subtype	Categorical	
IC ₅₀ for BMS-955176	Continuous	
IC50 Fold Change for BMS-955176	Categorical	< 1.0 1.0 to < 5 5 to < 10 10 to < 100 100 to < 500 ≥ 500

Table 7.3.2.1-3: Other Baseline Characteristics

Characteristic	Summarized as	Categories
Height	Continuous	
Weight	Continuous	
BMI	Continuous	
Hematology: Hemoglobin, Absolute Neutrophil Count(ANC), Platelets, White Blood Cell Count (WBC)	Categorical	Normal, Grade 1, Grade 2, Grade 3, Grade 4
Liver Function Tests: Alanine Aminotransferase (ALT), Aspartate Aminotransferase (AST), Albumin, serum, low Alkaline Phosphatase, Total Bilirubin	Categorical	Normal, Grade 1, Grade 2, Grade 3, Grade 4
Enzymes: Creatinine Kinase (CK), Lipase	Categorical	Normal, Grade 1, Grade 2, Grade 3, Grade 4
Renal Function Tests: Creatinine, Creatinine Clearance (eGFR), Uric Acid	Categorical	Normal, Grade 1, Grade 2, Grade 3, Grade 4
Electrolytes: Bicarbonate, serum, low Calcium, serum, high Calcium, serum, low Potassium, serum, high Potassium, serum, low Sodium, serum, high Sodium, serum, low	Categorical	Normal, Grade 1, Grade 2, Grade 3, Grade 4,
Fasting Lipids: Total Cholesterol, LDL-Cholesterol, Triglycerides	Categorical	Normal, Grade 1, Grade 2, Grade 3, Grade 4
Fasting Glucose: Glucose, serum, high Glucose, serum, low	Categorical	Normal, Grade 1, Grade 2, Grade 3, Grade 4,

Baseline laboratory values are graded using the DAIDS Toxicity Grades tables as presented in Appendix 3 of the protocol.

Physical examination findings at baseline will be summarized by randomized treatment group and overall.

7.3.2.2 Pre-treatment CDC Class C AIDS Events

Pre-treatment CDC Class C AIDS events (as collected on the AIDS defining events CRF page) will be summarized by as-treated treatment arm and overall for the treated subjects. Pre-treatment events are those with an onset before the start of any study therapy. Documented clinical diagnoses are used to define AIDS (see Protocol Appendix 2).

7.3.2.3 Previous Medication

Previous medications are defined as those medications that are taken before the start of any study therapy. Previous medications will be summarized by as-treated treatment arm and overall for the treated subjects. Medications are presented alphabetically by anatomic class, therapeutic class and generic name. The WHO dictionary is used to code the non-study medication.

7.3.2.4 Baseline Resistance

Phenotypic resistance to a drug is defined as a fold change (i.e., ratio of the 50% inhibitory concentration (IC₅₀) of the clinical isolate to the IC₅₀ of the reference strain) which is greater than the cut-off for reduced susceptibility.

The number of subjects with phenotypic resistance at baseline will be summarized for all treated subjects, for subjects who had on-study resistance testing done and for treated subjects that are identified as protocol defined virologic failures (see Protocol Section 5.4.1.3) using the following, mutually exclusive categories:

- No resistance to drugs in any class
- ≥ 1 NRTI
- ≥ 1 NNRTI
- ≥ 1 PI
- ≥ 1 INI
- ≥ 1 NRTI and ≥ 1 NNRTI
- ≥ 1 NRTI and ≥ 1 PI
- ≥ 1 NRTI and ≥ 1 INI
- ≥ 1 NNRTI and ≥ 1 PI
- ≥ 1 NNRTI and ≥ 1 INI
- ≥ 1 PI and ≥ 1 INI
- ≥ 1 NRTI and ≥ 1 NNRTI and ≥ 1 PI
- ≥ 1 NRTI and ≥ 1 NNRTI and ≥ 1 INI

- ≥ 1 NRTI and ≥ 1 PI and ≥ 1 INI
- ≥ 1 NNRTI and ≥ 1 PI and ≥ 1 INI
- ≥ 1 NRTI and ≥ 1 NNRTI and ≥ 1 PI and ≥ 1 INI

The number of subjects with phenotypic resistance will also be summarized by class and drug name.

The genotypic resistance profile at baseline will be summarized by treatment arm for all treated subjects, for subjects who had on-study resistance testing done and for treated subjects that are identified as protocol defined virologic failures. Tabulations will present genotypable isolates, those with PI substitutions from genotypable isolates, those with selected RT substitutions from genotypable isolates, and those with integrase substitutions from genotypable isolates using the most current version of the International AIDS Society-USA (IAS-USA) list (see [APPENDIX 2](#)). The genotypic resistance profile at baseline will also be summarized by baseline HIV subtype for all treated subjects.

In addition, baseline gag polymorphisms at positions 362, 364, 369 and 370 (relative to the wild type HxB2) will be summarized by treatment arm. This list of positions might be updated. The summary will report single mutations and combinations of mutations. The baseline gag polymorphisms at selected positions will also be summarized by baseline HIV subtype for all treated subjects.

Any deviation from the wild type virus (HxB2) in baseline gag sequencing will be summarized for treated subjects by treatment arm. This summary will also be provided by baseline HIV subtype.

The summaries for gag will be provided for treated subjects, for treated subjects who had on-study resistance testing done and for treated subjects that are identified as protocol defined virologic failures.

7.4 Extent of Exposure

Extent of exposure is presented for treated subjects by as-treated treatment arm.

7.4.1 Study Therapy

Time (in days) on study therapy will be summarized by treatment arm. Time on study therapy is defined as the difference between the earliest last dose date of any component of the treatment arm and the first dose date of study treatment plus 1 day.

Time on study therapy and average daily dose will be summarized for each individual drug component by treatment arm. Time on an individual drug component is defined as the number of days between the first dose date and the last dose date of the drug. The average daily dose is the total amount of drug in grams divided by the number of days between the first dose date and the last dose date of the drug.

The time on BMS-955176 and average daily dose after the switch to the continuation dose will be summarized for subjects who switched to the continuation dose after Week 24, rather than starting on the continuation dose at the time of randomization. Time on BMS-955176 continuation dose is defined as the difference between the last dose date of continuation dosing and the first dose date of continuation dosing plus 1 day.

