8.4 Study Therapy

Time on therapy for each individual drug component is calculated from the first and last dates of dosing, regardless the interruptions. The first date of dosing is the minimum of the dosing start dates, and the last date of dosing is the maximum of dosing stop dates.

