3.3.1. Tables

Number	Title	BMS Table number/File Name/BMS Template
3.1	Extent of Exposure to BMS-955176 Time on Therapy Modified Treated Subjects	Table S.4.1.1A / rt-ex-bmss1.lst / SS_EX_T_001
3.2	Extent of Exposure to Tenofovir Time on Therapy Modified Treated Subjects	Table S.4.1.1B / rt-ex-tdfs1.lst / SS_EX_T_001
3.3	Extent of Exposure to Atazanavir Time on Therapy Modified Treated Subjects	Table S.4.1.1C / rt-ex-atvs1.lst / SS_EX_T_001
3.4	Extent of Exposure to Dolutegravir Time on Therapy Modified Treated Subjects	Table S.4.1.1D / rt-ex-dtgs1.lst / SS_EX_T_001
3.5	Extent of Exposure to Ritonavir Time on Therapy Modified Treated Subjects	Table S.4.1.1E / rt-ex-rtvs1.lst / SS_EX_T_001
3.6	Extent of Exposure to Treatment Regimen Time on Therapy Modified Treated Subjects	Table S.4.1.1F / rt-ex-regimens1.lst / SS_EX_T_001
3.7	Adverse Events Overall Adverse Events Summary Modified Treated Subjects	Table S.6.7.1 rt-ae-overallsums1.lst SS_AE_T_001
3.8	Summary of Serious Adverse Events Modified Treated Subjects	Table S.6.2.1A / rt-ae-saes1.lst / GS_AE_T_X_001
3.9	Summary of Serious Adverse Event With Death As An Outcome Modified Treated Subjects	Table S.6.2.1C / rt-ae-saeldeaths1eu.lst / GS_AE_T_X_001

CONFIDENTIAL

AI468038/205891

Number	Title	BMS Table number/File Name/BMS Template
3.10	Summary of Drug Related Serious Adverse Event With Death As An Outcome Modified Treated Subjects	Table S.6.2.2D / rt-ae-relsaedeaths2eu.lst / GS_AE_T_X_001
3.11	Listing of Serious Adverse Events Modified Treated Subjects	Table S.6.2.1E / rl-ae-saes1.lst / GS_AE_L_S_001
3.12	Death Listing Enrolled Subjects	Table S.6.1.1 / rl-ae-deaths1.lst / SS_AE_L_001
3.13	Summary of Adverse Events Leading to Discontinuation of Study Medication Modified Treated Subjects	Table S.6.3.1A / rt-ae-aediscs1.lst / GS_AE_T_X_001
3.14	Listing of Adverse Event Leading to Discontinuation of Study Medication Modified Treated Subjects	Table S.6.3.1C / rl-ae-discs1.lst / GS_AE_L_X_001
3.15	Summary of Non-Serious Adverse Events Occurring in at Least 5 Percent of Treated Subjects Modified Treated Subjects	Table S.6.5.1A / rt-ae-nsae5pcts1.lst / GS_AE_T_X_001
3.16	Summary of Grade 1 to 4 Adverse Events Modified Treated Subjects	Table S.6.5.1B / rt-ae-grade1to4s1.lst / GS_AE_T_X_001
3.17	Summary of Grade 2 to 4 Adverse Events Modified Treated Subjects	Table S.6.5.1C / rt-ae-grade2to4s1.lst / GS_AE_T_X_001

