4.4 Extent Of Exposure

4.4.1 Study Therapy and Treatment Compliance

Template SS_EX_T_001: Extent of Exposure Summary

	Group A N = XX	Group B N = XX	Group C N = XX	Group D N = XX
N	XX	XX	XX	XX
MEAN	XX.X	XX.X	XX.X	XX.X
MEDIAN	XX.X	XX.X	XX.X	XX.X
MIN , MAX	XX.X , XX.X	XX.X , XX.X	XX.X , XX.X	XX.X , XX.X
Q1 , Q3	XX.X , XX.X	XX.X , XX.X	XX.X , XX.X	XX.X , XX.X
STANDARD DEVIATION	XX.XX	XX.XX	XX.XX	XX.XX
MEAN DAILY DOSE (mg)	XXX.X	XXX.X	XXX.X	XXX.X

Parameter	Values
Template ID	SS_EX_T_001
Output File Name	rt-ex-bmss1.lst
Purpose	WK24S1, WK48S1, WK96S1, WK96S2
Table No.	Table S.4.1.1A
Title 1	Extent of Exposure to BMS-955176
Title 2	Time on Therapy
Title 3	Treated Subjects - Stage 1
Layout notes	Include Mean Daily Dose

Parameter	Values
Template ID	SS_EX_T_001
Output File Name	rt-ex-bmss2.lst
Purpose	WK24S2, WK48S2, WK96S2
Table No.	Table S.4.1.2A

Title 1	Extent of Exposure to BMS-955176
Title 2	Time on Therapy
Title 3	Treated Subjects - Stage 2
Layout notes	Include Mean Daily Dose

Parameter	Values
Template ID	SS_EX_T_001
Output File Name	rt-ex-tdfs1.lst
Purpose	WK24S1, WK48S1, WK96S1, WK96S2
Table No.	Table S.4.1.1B
Title 1	Extent of Exposure to Tenofovir
Title 2	Time on Therapy
Title 3	Treated Subjects - Stage 1
Layout notes	Include Mean Daily Dose

Parameter	Values
Template ID	SS_EX_T_001
Output File Name	rt-ex-tdfs2.lst
Purpose	WK24S2, WK48S2, WK96S2
Table No.	Table S.4.1.2B
Title 1	Extent of Exposure to Tenofovir
Title 2	Time on Therapy
Title 3	Treated Subjects - Stage 2
Layout notes	Include Mean Daily Dose

Parameter	Values
Template ID	SS_EX_T_001
Output File Name	rt-ex-atvs1.lst
Purpose	WK24S1, WK48S1, WK96S1, WK96S2
Table No.	Table S.4.1.1C
Title 1	Extent of Exposure to Atazanavir
Title 2	Time on Therapy
Title 3	Treated Subjects - Stage 1
Layout notes	Include Mean Daily Dose

Parameter	Values
Template ID	SS_EX_T_001
Output File Name	rt-ex-atvs2.lst
Purpose	WK24S2, WK48S2, WK96S2
Table No.	Table S.4.1.2C
Title 1	Extent of Exposure to Atazanavir
Title 2	Time on Therapy
Title 3	Treated Subjects - Stage 2
Layout notes	Include Mean Daily Dose

Parameter	Values
Template ID	SS_EX_T_001
Output File Name	rt-ex-dtgs1.lst
Purpose	WK24S1, WK48S1, WK96S1, WK96S2
Table No.	Table S.4.1.1D

Title 1	Extent of Exposure to Dolutegravir
Title 2	Time on Therapy
Title 3	Treated Subjects - Stage 1
Layout notes	Include Mean Daily Dose

Parameter	Values
Template ID	SS_EX_T_001
Output File Name	rt-ex-dtgs2.lst
Purpose	WK24S2, WK48S2, WK96S2
Table No.	Table S.4.1.2D

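### SAP Section 7.4.1 adds a day when counting regimen and continuation-dose time but not for component time or the average-daily-dose divisor, and Section 8.4 does not settle which count applies

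*SAP*

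**What the plan says.** SAP Section 7.4.1 (Study Therapy) defines several quantities close together.

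- **Regimen time** runs from the start to the earliest final dose, and a day is added. It is worded in terms of "any component of the treatment arm and the first dose date of study treatment plus 1 day".
- **Component time** is "defined as the number of days between the first dose date and the last dose date of the drug". No day is added.
- **Average daily dose** uses the same count, ending at the drug's final dose, as its divisor: "The average daily dose is the total amount of drug in grams divided by the number of days between the first dose date". No day is added.
- **Continuation-dose time** is the difference between "the last dose date of continuation dosing and the first dose date of continuation dosing plus 1 day".

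An average daily dose after the switch to the continuation dose is also called for, but it is given no divisor of its own.

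SAP Section 8.4 returns to component time: "Time on therapy for each individual drug component is calculated from the first and last dates of dosing, regardless the interruptions". It takes the earliest start and the latest stop of each drug, and does not say whether both end days count.

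The exposure shell in the data presentation plan (Section 4.4.1, template SS_EX_T_001) has a row labelled "MEAN DAILY DOSE (mg"), whereas Section 7.4.1 gives the total in grams. The final-analysis appendix (Section 3.3.1) keeps component Tables 3.1 to 3.5, the first being "Extent of Exposure to BMS-955176 Time on Therapy Modified Treated Subjects", next to regimen Table 3.6. All six use that template.

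**The concern.** The extra day is written out for the regimen and the continuation dose and is absent between them for the components. A programmer who follows the text will take the absence as intended. The numerator then includes the doses of both the first and the last day, while the divisor leaves one of those days out. The average daily dose is too high by a factor that grows as exposure shortens, and it cannot be computed for a subject dosed on one day only. Regimen and component durations, reported in neighbouring tables, would also rest on different counts. Two programmers could produce different exposure tables from the same text.

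**Working it through.** The SAP states no numerical value here, so there is no figure to reproduce. The check follows the definitions.

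**Inputs**
- Dose for illustration: 120 mg once daily (SAP Section 2.1, Arm 1).
- First dose day is study Day 1. Target days for Weeks 24, 48 and 96 are 169, 337 and 673 (Section 8.1.2, Table 8.1.2-1).
- Shortest possible exposure: one dose, which is enough to be a treated subject (Section 6.3).

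**Formulas.** Let D be the number of dosing days counted inclusively, with one dose on each.
- Literal rule: 120 × D/(D − 1).
- Inclusive rule: 120 × D/D = 120 at every D.
- Inflation: D/(D − 1) − 1 = 1/(D − 1), the same for every once-daily component.

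| D (days) | Literal divisor | Literal average (mg) | Inflation |
|---|---|---|---|
| 1 | 0 | undefined | – |
| 2 | 1 | 240.0 | 100% |
| 7 | 6 | 140.0 | 16.7% |
| 15 | 14 | 128.6 | 7.1% |
| 28 | 27 | 124.4 | 3.7% |
| 169 (Week 24) | 168 | 120.71 | 0.60% |
| 337 (Week 48) | 336 | 120.36 | 0.30% |
| 673 (Week 96) | 672 | 120.18 | 0.15% |

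**Missed doses.** With m missed days between the first and last dose, the literal average is 120 × (D − m)/(D − 1). It is above 120 mg only when m = 0. At D = 169:
- m = 1 gives 120 × 168/168 = 120.0 mg.
- m = 2 gives 120 × 167/168 = 119.3 mg.
- m = 17 gives 120 × 152/168 = 108.57 mg, against 120 × 152/169 = 107.93 mg inclusively.

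The ratio of literal to inclusive average stays at 169/168 throughout.

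**Effect on an arm mean (assumed mix).** Take 40 fully adherent subjects, 39 at D = 169 and one at D = 2. The literal mean is (39 × 120.714 + 240)/40 = 123.7 mg, against 120 mg inclusively. The single early stopper accounts for most of the gap.

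**Component against regimen time.** Let the regimen start on Day 1 and let the earliest last dose of any component fall on Day E. Regimen time is E days. On the literal rule, a component that also starts on Day 1 has:
- E − 1 days if it stops on Day E, one day less than the regimen;
- E days if it stops on Day E + 1, equal to the regimen;
- more than E days if it stops later still.

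**The case against.** **The wording may not mean D − 1.** The definitions with the extra day are worded as a difference between two dates, a subtraction that needs correcting. The component definition speaks of a number of days between two dates, which someone could count inclusively. This stands as a possibility. The neighbouring definitions still make the literal reading the natural one, and Section 8.4 does not decide it. If the inclusive count was meant, the text should say so.

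**The effect is small and its reach narrow.** Both points stand. At the planned durations the inflation is 0.15% to 0.60%. The primary endpoint, the futility test and the Kaplan-Meier analysis of time on therapy (Section 7.4.2) do not use this divisor. Exposure for adverse event rates follows separate sponsor algorithms (Section 7.6.12).

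**Stronger readings that the document does not support:**
- A reader might infer that an arm's mean daily dose would generally exceed its assigned dose. For an individual subject, that needs dosing with no gaps; two missed doses in 169 days already bring the literal average below 120 mg.
- A reader might infer that component time is always one day shorter than regimen time. That holds only for a component that starts on the regimen's first dose date and stops on the earliest last dose date.
- A reader might infer that one-day subjects would drop out of the mean. The SAP does not say how a zero divisor is handled.
- A reader might infer that early closure of the study made short exposures common. The documents give no actual durations.

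**Grams against mg is minor.** This also stands: the shell labels its unit, so a reader of the table is not misled.

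**Conclusion.** The concern holds as an inconsistent day-count definition in SAP Sections 7.4.1 and 8.4. The SAP prints no wrong number. On the literal reading, average daily dose is inflated by D/(D − 1) against the true average. This is negligible for subjects who reach Week 24 or beyond, material for those who stop within the first weeks, and undefined for one day of dosing, which the treated population allows. These sizes assume once-daily dosing and a divisor programmed without the extra day. The consequence is confined to descriptive exposure tables. It is a worthwhile correction of low severity.

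**What to change.** In SAP Sections 7.4.1 and 8.4, define time on each component as last dose date minus first dose date plus one day. Use that count as the divisor of average daily dose, and state that the same applies to the average daily dose after the switch, using the continuation-dose dates. Give the total amount of drug in mg so that the text matches the shell. With this divisor a fully adherent subject averages exactly the assigned dose at every duration, including one day.

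The cost is a sentence in each of two sections and a small change to the exposure program, with no new data. If the tables have already been programmed, check which count the code uses and align text and code. The change concerns calculation only and leaves dosing untouched.

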7.4.2 Discontinuation of Study Therapy

Time (in days) on any study therapy will be described by a Kaplan-Meier curve and life table with the Kaplan-Meier estimates.

Discontinuations from study therapy are considered events in this analysis. For subjects who have not discontinued, time on study therapy is censored at the last recorded dose stop date of any study therapy. For the purpose of this analysis, we will consider the start date and event/censor date regardless of any interruptions.

7.4.3 Interruption or Delay of Study Therapy

Interruptions of study therapy greater than 3 consecutive days will be summarized by treatment arm and for each drug in the regimen. Interruptions are identified from complete dosing records in which either the number of units per day or the number of doses per day is zero.

7.4.4 Concomitant Therapy

Concomitant medications are defined as those taken at any time on or after the start date of study therapy and before or on the last dose date of study therapy. Concomitant medications will be summarized by treatment arm and overall for the treated subjects. Medications are presented alphabetically by anatomic class, therapeutic class and generic name. The WHO dictionary is used to code the non-study medication.

7.5 Efficacy

Efficacy endpoints are evaluated for treated subjects by as-randomized treatment arm during the treatment period through a specific analysis week. Measurements obtained on treatment and before or on the analysis week date (see [Section 8.2](#)) will be included.

7.5.1 Primary Efficacy Endpoint: Proportion of Subjects with Plasma HIV-1 RNA < 40c/mL at the Week 24 Snapshot

The primary efficacy endpoint is the proportion of subjects with plasma HIV-1 RNA < 40c/mL at the Week 24 snapshot. The primary analysis will be based on a modified ITT (mITT) approach. A sensitivity analysis will be conducted using an observed values approach. The two approaches will be implemented as follows:

- Modified ITT: The numerator will be based on subjects with plasma HIV-1 RNA < 40c/mL at Week 24. The denominator will be based on all treated subjects.

- Observed values: Similar to the mITT approach, the numerator will be based on subjects with plasma HIV-1 RNA < 40c/mL at Week 24. However, the denominator will be based on treated subjects with plasma HIV-1 RNA at Week 24.

Response rates will be tabulated by treatment arm with exact (Clopper-Pearson) binomial 95% confidence intervals.

This endpoint is assessed with the snapshot algorithm. The snapshot algorithm is described in detail in Appendix 1 of the CDER (2013) draft guidance¹ on developing antiretroviral drugs (see also [APPENDIX 1](#) of this SAP). If the draft guidance is superseded, and development timelines permit any needed changes, the instructions from the new guidance should be followed.

The main principle of the snapshot analysis is that the primary efficacy endpoint is intended to be primarily a virologic endpoint and not a clinical endpoint. The snapshot algorithm follows a “Virology First” hierarchy. The hierarchy for assessing percentages is “HIV-1 RNA < Limit of Detection” or “HIV-1 RNA ≥ Limit of Detection” first for any given time window followed by reasons for “No Virologic Data in the Window”.

The snapshot approach algorithm is based on the event occurring within a visit window which is outlined in [Section 8.1](#).

Optimized Background Therapy (OBT) Substitutions

Changes in background therapy are not allowed per protocol. Subjects who do change their dose for TDF in the event of treatment-limiting renal toxicity will be considered virologic failure if they have HIV-1 RNA > 40 at the time of the change.

Movement of a subject to the continuation dose of BMS-955176 will not be a cause for classifying a subject as a virologic failure.

The snapshot analysis must include a table that is of the same format shown in Table B (line 1209) of the draft guidance. A more detailed presentation that breaks down the FDA categories into finer detail, may also be provided. The snapshot analysis will be accompanied by a detailed listing that facilitates finding the patients in each category described in the table.

The snapshot analysis is supplemented by a Time to Loss of Virologic Response (TLOVR) analysis at Weeks 24. Analyses are presented for the randomized treatment groups both separately and combined. TLOVR analyses are described in [APPENDIX 3](#).

